Examination of Psychological Tools and Tracking in an Online Intervention for Type 2 Diabetes

NCT03037528

Document Date: 01-26-17

Protocol, analysis plan, and consent form

Nutritional management is one of the cornerstones of type 2 diabetes treatment, as dietary changes can lead to glycemic control and the reduced need for anti-glycemic medications [1]. Several dietary approaches are recommended for type 2 diabetes, including a very-low carbohydrate (VLC) diet. For example, a recent report by the ADA's Nutrition Review Committee noted the benefits of a reduced-carbohydrate diet and updated the policy guidelines to recommend that for people with type 2 diabetes "...not meeting glycemic targets or where reducing anti-glycemic medications is a priority, reducing overall carbohydrate intake with a low- or VLC eating plan is a viable approach" [2]. Physiologically, carbohydrate intake raises blood glucose levels, which in turn increases insulin secretion from the pancreas. Insulin then inhibits lipolysis and the subsequent release of fatty acids from cells [3]. Numerous studies indicate that a reduced-carbohydrate diet is particularly effective at improving glycemic control, reducing the need for glucose-lowering medications, increasing weight loss, and bringing about other positive health outcomes in type 2 diabetes [4-7].

However, long term adherence to any diet can be challenging, and it is not clear which strategies could help people maintain dietary changes. In this trial, as we screened three potentially effective strategies using a full-factorial design. This was informed by the Multiphase Optimization Strategy (MOST) framework [8]. This approach suggests that before conducting clinical trials of multi-component interventions, particular components of the intervention should be tested, especially those which might be costly, burdensome, or simply have not been previously tested enough to be clearly appropriate for a particular intervention. Such an approach is becoming more common in intervention development, e.g., in the areas of weight loss [9], physical activity promotion [10], and in our previous pilot study of VLC diet for type 2 diabetes [11]. In this case, we tested three low-cost strategies that varied in their burdensomeness and level of previous testing in this intervention [12].

In the current trial, we examined three supplemental strategies that we expected may improve glucose control over a 12-month period. The first was dietary self-monitoring, varying whether participants were encouraged to keep track of what they were eating every day versus monthly (in bursts of three days every 4 weeks). Weight loss trials involving dietary changes typically encourage daily dietary self-monitoring, as this can help people to become more aware of their dietary adherence, and it tends to be associated with weight loss [13]. However, participants commonly dislike daily monitoring and their adherence to it tends to fade over time [14, 15]. Thus, we compared encouragement to self-monitor diet daily vs. less often, which may still be able to help participants self-regulate, but to do so in a less burdensome manner.

The second strategy we included was mindfulness, varying whether or not we taught participants how to increase their experience of mindfulness and mindful eating. We included exercises to increase awareness of the physical, cognitive, and emotional triggers of overeating; the awareness of internal cues that signal hunger, fullness, and taste satisfaction; "surfing" the urges to reduce emotional eating; and the cultivation of healthier alternatives [16, 17]. These approaches aim to help participants become more aware of their hunger-related bodily sensations, food cravings, and eating triggers, so that they can choose to respond more deliberately. Previous research shows that mindful eating helps reduce emotional eating, an important barrier for dietary adherence [18, 19]; increased mindful eating was correlated with decreased fasting glucose levels in participants of a mindful eating weight loss intervention [20]; and mindful eating was a mediator of the effect of a mindful eating intervention for weight loss [19]. However, mindfulness strategies can backfire, sometimes leading to greater anxiety and

depression [21], and the strategies require extra time and attention, which could be burdensome.

The third strategy was positive affect skills training, aiming to increase the frequency that participants experienced positive emotions, such as focusing on gratitude, using one's personal strengths, conducting acts of kindness, and savoring positive experiences [22]. To adhere to a behavioral intervention, participants need to effectively cope with inevitable stressors. According to the revised Stress and Coping Theory [23, 24], positive affect can serve as a psychological "time-out" from stress and increase adaptive coping [25-27], and interventions that help increase the experience of positive affect have been able to reduce depressive symptoms [28]. Additionally, hedonic theories of behavior propose that people do more of what they enjoy [29], possibly because positive emotional responses to behaviors increase the motivation and nonconscious desire to engage in those behaviors [30, 31]. For example, previous research has found an association between higher eating plan satisfaction rates and adherence [32, 33]. However, positive affect skill interventions may have small to little impact on outcomes [34], and they take time to implement, which could be burdensome.

The primary aim of this study was to assess whether several supplementary strategies (daily versus monthly dietary self-monitoring, mindfulness skills, and positive affect skills) could improve outcomes in this VLC intervention with adults with type 2 diabetes.

### **Procedure**

The institutional review board at the University of Michigan approved the study materials (HUM00115537). We registered this study with clinicaltrials.gov (NCT03037528). We placed advertisements or notices of the research online (including Craigslist, University of Michigan's web-based portal for clinical trials, and ResearchMatch) and sent invitation letters to potentially eligible participants identified from health plan records at Michigan Medicine. Interested participants were directed to the study website, which contained the University of Michigan logo, pertinent study information, and a link to an online self-report screening survey (Qualtrics.com). Those who were eligible for further screening based on their survey responses were asked to provide online electronic consent for the trial and subsequently to undergo a second online survey (Qualtrics) which included the eight-item Patient Health Questionnaire (PHQ-8) to measure depressive symptoms [35]; a self-administered glycated hemoglobin (HbA1c) test from DTI Laboratories, Inc; and 3 days of dietary tracking on MyFitnessPal. We also mailed these individuals a body weight scale that connects to its own cellular network (BodyTrace) and automatically reports weights to the study team. Those who met all entry criteria (below) were invited to participate in the trial.

Participants were eligible to participate if they were aged 21 to 70 years, had a baseline HbA1c of 6.5% or higher, had a BMI of 25-45 kg/m^2 (based on self-reported height and measured weight from the study-provided scale), had regular access to the internet, were willing to check their email at least once a week, were comfortable reading and writing in English, had no potentially serious comorbidities, such as liver or kidney failure, were planning on living in the United States for the duration of the trial, were not vegetarian or vegan, and were not on weight-loss medications, and were not taking warfarin, Coumadin, or lithium. We also excluded people who were pregnant or breastfeeding, had an untreated thyroid condition, had an untreated mental health condition, had had weight loss surgery in previous year, or were undergoing cancer treatments. Given that this study was conducted remotely, to mitigate the risk of hypoglycemia, we excluded participants who reported taking any glucose-lowering medication other than metformin.

This 2x2x2 full factorial experimental design examined the impact of three experimental, 2-level components. Once all baseline measurements had been completed, study staff randomized participants to one of the eight experimental conditions (see Table 1) using a computer program to reveal the next assignment. The order was created using block randomization procedures, with blocks randomly allocated to size 8 or 16 and with the seed numbers of 64655102233242, 64655183677600 from the website Sealed Envelope (Sealed Envelope Ltd. 2015. Create a blocked randomization list. [Online] Available from: <https://www.sealedenvelope.com/simple-randomiser/v1/lists> [Accessed 14 Jan 2017]). We stratified randomization by gender.

All tested combinations of the three intervention enhancement strategies.

	Experimental components		
Combination	Tracking frequency	Mindfulness	Positive affect
1	Daily	Yes	Yes
2	Daily	Yes	No
3	Daily	No	Yes
4	Daily	No	No
5	Monthly	Yes	Yes
6	Monthly	Yes	No
7	Monthly	No	Yes
8	Monthly	No	No

### ***The Basic Intervention***

Once participants were assigned to one of eight groups, they were e-mailed links to online intervention materials throughout the 12-month intervention, weekly for the first 4 months and then biweekly for the remaining 8 months, for a total of 32 emails. Each of the 32 batches of materials focused on a different topic related to following a VLC diet. Emailed links connected participants to a) a short survey to assess intervention-related dietary adherence and any health concerns, b) a short, embedded video teaching class topics (such as managing their diet during holidays or shifting particular meals to be VLC, etc.), c) downloadable handouts to accompany the video, and d) links to external online resources supporting class topics. Transcripts of the embedded videos were also provided.

The basic intervention included several components that all participants received, regardless of assignment. We taught participants to eat a VLC diet per our previous protocol [11], reducing carbohydrate intake to between 20-35 non-fiber grams of carbohydrates a day with the goal of achieving nutritional ketosis, defined as a positive urine dipstick (Bayer Ketostix), which measures ketone acetoacetate. A VLC diet consists of meats, cheeses, eggs, healthy fats, nuts, seeds, and low-carbohydrate vegetables, eliminating starchy and sugary foods. Participants also had email access to a diet coach whenever they had questions and would receive prompt replies with support and resources and who emailed participants a minimum of every two weeks. Coaches have generally been found to be effective additions to behavioral interventions [36]. Participants received a scale at the start of the intervention and were asked participants to track their body weight regularly. Coaches used this information to monitor participant success and tailor support. Beginning in week 6 of the intervention, we provided goals for physical activity and sleep. Using the Diabetes Prevention Program [37] as a guide, participants were encouraged to be physically active for at least 150 minutes a week. Participants were also encouraged to practice sleep hygiene with the target of 7-9 hours total sleep per day. To encourage the adoption and maintenance of the new intervention-related behaviors, participants

were sent text messages up to 5 times a week about the targeted behaviors and skills, depending on which group they had been assigned to, as reminders about targeted behaviors are tied to greater behavioral adherence [38]. To help participants change their dietary patterns and increase their self-efficacy around preparing and eating new foods, we mailed cookbooks to participants: *Keto Living 3 Cookbook: Lose Weight with 101 All New Delicious and Low Carb Ketogenic Recipes* [39] at baseline, *Bacon & Butter, the Ultimate Ketogenic Diet Cookbook* [40] at month 3, *The Wicked Good Ketogenic Diet Cookbook: Easy, Whole Food Keto Recipes for Any Budget* [41] at month 6, and *The Everyday Ketogenic Kitchen With More Than 150 Inspirational Low-Carb, High-Fat Recipes to Maximize Your Health* [42] at month 10.

### **Experimental Components**

In addition to the core intervention, we randomized participants to one of eight possible combinations of the three supplemental components; tracking frequency, positive affect, and/or mindfulness. For each, the program materials were altered, including different content added to the videos, handouts, and text messages. Each factor was selected for its potential to improve participants' ability and interest in adhering to the assigned diet over 12 months.

**1) Daily vs. monthly self-monitoring of dietary intake.** We asked participants to track their diet using the free web-based and/or mobile application MyFitnessPal [43], which has a wide variety of foods in its database that are common to the diet assigned in this trial (reducing participant burden and increasing accuracy). Half of participants were asked to track their diet daily and the other half were asked to track their diet monthly (for 3 days every 4 weeks).

**2) Training vs. no training in mindfulness.** Half of participants were taught mindfulness, including mindful eating, how to practice it in everyday life, research behind the skills, how the skills are expected to help, and targeted suggestions for practicing the skills until the next lesson. We asked participants to focus on consciously savoring their food, eating more slowly, and noticing the textures, flavors, and aromas of their food more carefully. For example, they were asked to practice slowly savoring their food with a snack and were then encouraged to practice this skill with at least one meal a day over the next week.

**3) Training vs. no training in positive affect skills.** Half of participants were taught diet-focused positive affect skills, how to practice them in everyday life, the supporting research, how and why the skills are expected to help, and targeted suggestions for practicing the skills. We taught participants ways to feel more positive affect, for example, by focusing on gratitude, thinking about and applying their personal strengths, applying their personal strengths.

### **Assessments**

We measured outcomes at baseline and at 4, 8, and 12 months after baseline. As an incentive for continued participation, we paid participants US \$25 for completing their outcome measurements at 4 months, US \$25 at 8 months, and US \$50 at 12 months. At each period, we measured glycemic control with an at-home kit, body weight using the scale we had mailed to participants (participants were asked to stand on the scale twice in five minutes and we used the average weight), and depressive symptoms using the PHQ-8 [35].

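### Does the absence of any described medication recording after baseline undermine the HbA1c comparison between factor levels?

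*Combined protocol and SAP*

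**What the plan says.** The Assessments section gives four time points (baseline and months 4, 8 and 12) and three measures: "At each period, we measured glycemic control with an at-home kit, body weight using the scale we had mailed to participants", and depressive symptoms by PHQ-8. Medication is not among them.

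Glucose-lowering medication appears in two other places. The opening background uses it as rationale: "dietary changes can lead to glycemic control and the reduced need for anti-glycemic medications", and later "reducing the need for glucose-lowering medications, increasing weight loss, and bringing about other positive health outcomes in type 2 diabetes". The Procedure section uses it as a self-reported entry rule: "we excluded participants who reported taking any glucose-lowering medication other than metformin". Everyone therefore enters on metformin or on no glucose-lowering drug, and no section says what happens to medication afterwards.

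Two recurring contacts are described under The Basic Intervention. One is "a short survey to assess intervention-related dietary adherence and any health concerns". The other is a diet coach "who emailed participants a minimum of every two weeks". Neither is said to ask about medication. The Statistical analysis section consists of two-sided t-tests and Cohen's d, with no mention of medication.

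**The concern.** The background treats better glucose control and reduced medication as two results of one mechanism. The components were "three supplemental strategies that we expected may improve glucose control over a 12-month period", and the Experimental Components section says each was chosen to help adherence to the diet. If a component works, participants at that level may cut back medication more often, or start it less often, and their HbA1c then understates what the diet did. The entry rule limits drugs at baseline but not changes after randomization.

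What is at stake is how a small or null difference is read. The plan says of one component that "positive affect skill interventions may have small to little impact on outcomes", so such a result is foreseeable. Without medication data by factor level, it could mean no effect or an effect partly offset by medication.

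**Working it through.** The plan gives no sample size, SD, effect size or power, so there is no figure of its own to reproduce. The check asks how much a medication response could hide, and whether the missing data would show it. All inputs below are assumptions.

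**Inputs**
- HbA1c before any medication change is normal, with SD 1.2 and means of 7.0 and 6.7 at the two factor levels (true difference 0.30).
- 70% are on metformin.
- Of metformin users below 6.5%, 30, 50 or 80% reduce.
- Of all participants above 8.0%, 0, 25 or 50% start or increase.
- Each change moves HbA1c by 0.5 or 1.0 points.
- This gives 3 × 3 × 2 = 18 combinations.

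**Step 1: share of participants who change medication**
- Below 6.5%: Φ((6.5 − 7.0)/1.2) = 0.338 and Φ((6.5 − 6.7)/1.2) = 0.434, a difference of 0.0954.
- Above 8.0%: 1 − Φ((8.0 − 7.0)/1.2) = 0.202 and 1 − Φ((8.0 − 6.7)/1.2) = 0.139, a difference of 0.0630.
- Difference in reducers: 0.7 × 0.3 × 0.0954 = 0.020 up to 0.7 × 0.8 × 0.0954 = 0.053.
- Difference in starts or increases: 0 up to 0.5 × 0.0630 = 0.0315.
- Combined: 2.0 to 8.5 percentage points.

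**Step 2: masked effect** = points per change × combined difference
- Smallest: 0.5 × 0.020 = 0.010, leaving 0.290.
- Largest: 1.0 × (0.0534 + 0.0315) = 0.085, leaving 0.215.
- The median over the 18 combinations is 0.034, or about 11% of the effect. The range is 3 to 28%.
- For a true effect of 0.1, the masked part is 0.003 to 0.029. For a true effect of zero it is zero, because medication here responds only to HbA1c.
- Varying the metformin share from 30 to 90% and the mean from 6.5 to 7.5 gives 0.003 to 0.100 of the 0.30.

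**Step 3: effect on the planned statistics.** The response pulls both tails inward, so the SD must be recomputed in the same model. It falls from 1.2 to between 0.95 and 1.17.
- Without medication change: d = 0.30/1.2 = 0.250.
- Smallest masking: 0.290/1.167 = 0.248.
- Largest masking: 0.215/0.954 = 0.225.
- The median is 0.244.
- Two-sided t-test at α = 0.05, equal halves: at an assumed N = 200, power is 42.1% without masking and 35.5 to 41.6% with it. At N = 80 it is 19.7% and 16.9 to 19.5%.

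**Step 4: what a medication table could show.** The 95% half-width for a difference in reducers is 1.96 × √[p₁(1 − p₁)/n + p₂(1 − p₂)/n], with n = N/2.

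| Reducers at the two levels | Difference | Half-width, N = 200 | Half-width, N = 80 |
|---|---|---|---|
| 7.1% v 9.1% | 2.0 points | 7.6 points | 12.0 points |
| 19.0% v 24.3% | 5.3 points | 11.4 points | 18.0 points |

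Every half-width exceeds every modelled difference in reducers.

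**The case for a change.** The strongest reply is that the model may be too mild. If the share changing medication differed by 20 percentage points between levels and each change moved HbA1c by 1.0 point, the offset would be 0.20 × 1.0 = 0.20. A true 0.30 would then appear as 0.10, and a true 0.20 as zero. A 20-point difference is also larger than any half-width in the table above, so medication data would reveal it. Recording would have cost one survey item at contacts that already existed, and medication reduction is a benefit the plan itself names.

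The cost argument and the value of knowing stand. The size does not carry over. In a model where medication follows HbA1c and the true difference is 0.30, the combined difference in changes is 2.0 to 8.5 points. All participants get the same basic diet programme, so only the between-level part counts. A 20-point gap would need a component that acts on medication use directly. Such an effect could run in either direction, so the statement that a component with no dietary effect shows no HbA1c difference holds only when medication responds to HbA1c alone. Even then, the comparison by assigned level remains a valid effect of assignment.

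The document also shows only that recording is not described. It is a condensed account in the past tense, and the health-concern surveys or coach emails may hold some medication information.

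**Conclusion.** No change to the plan is called for. The observation is accurate: post-baseline medication recording is not described. But the planned t-test on HbA1c regardless of medication answers a legitimate question, and recording medication would not alter it. Under the base-case assumptions, d moves from 0.250 to 0.225 at worst. Power at N = 200 drops by at most 42.1 − 35.5 = 6.6 percentage points, so a real effect is modestly attenuated and not turned into a null one. At these assumed sample sizes, low power limits interpretation far more than masking does.

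The extra table would change no result and could exclude only a large imbalance. With follow-up apparently complete, all that remains is a matter for the trial report: show any medication information already held, or note that HbA1c differences cannot be separated from medication change. A careful analyst would do this without an instruction in the plan.

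The conclusion rests on assumed values for metformin use, HbA1c distribution, response to HbA1c and sample size. It would weaken if a component changed medication use directly and strongly.

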### **Statistical analysis**

We conducted two-sided *t*-tests to assess statistical significance and effect size (Cohen's *d*).

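### The analysis plan is a t-test with no analysis set, missing-data method, baseline adjustment or model across visits, which loses precision and leaves component effects open to drop-out bias

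*Combined protocol and SAP*

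**What the plan says.** The Statistical analysis section is a single sentence: "We conducted two-sided *t*-tests to assess statistical significance and effect size", the effect size being Cohen's d. It does not say which visit is tested, whether follow-up values or changes from baseline are compared, who is included, or what happens to missing values. No other section supplies these points.

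The design collects much more than a two-sample comparison uses:

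- Assessments: "We measured outcomes at baseline and at 4, 8, and 12 months after baseline". The outcomes are HbA1c by home kit, body weight and PHQ-8.
- Introduction: "we examined three supplemental strategies that we expected may improve glucose control over a 12-month period".
- Procedure: "We stratified randomization by gender". A baseline HbA1c is an entry criterion, so every randomised participant has one.

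The only text bearing on missing outcomes concerns trial conduct: "As an incentive for continued participation, we paid participants", in amounts of $25, $25 and $50 at months 4, 8 and 12.

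**The concern.** Read in the usual way, the plan is a t-test at month 12 among those with a month-12 result. Two things follow.

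First, precision is lost whatever the reason for drop-out. A test on month-12 values ignores baseline, and either form of the test discards the month 4 and 8 results of people who left. This is a screening trial of components, so lower precision means a useful component is more easily missed.

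Second, bias is possible. It arises if drop-out depends on response and that dependence, or the amount of response-related loss, differs between the levels of a component. The introduction gives reasons why retention might differ. On tracking: "participants commonly dislike daily monitoring and their adherence to it tends to fade over time". On mindfulness: "the strategies require extra time and attention, which could be burdensome". On positive affect training: "they take time to implement, which could be burdensome". This makes differential loss plausible. It does not show that it occurred, or that it was related to response.

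**Working it through.** **Inputs.** The documents state no sample size, SD, correlation, effect size or drop-out rate, so there is no figure of the plan's own to reproduce. Everything below is assumed: 120 participants (60 at each level of a component), HbA1c SD 1.2, baseline to follow-up correlation 0.5, correlation between follow-ups 0.7, two-sided 5% tests. From the documents come the visits, the two-level components and the t-test.

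**Baseline adjustment, by formula.** Let r be the baseline to follow-up correlation. In large samples the variance of the adjusted estimate is (1 - r²) times that of a t-test on values, and (1 + r)/2 times that of a t-test on change.

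| r | vs values, 1 - r² | vs change, (1 + r)/2 |
|---|---|---|
| 0.3 | 0.91 | 0.65 |
| 0.5 | 0.75 | 0.75 |
| 0.7 | 0.51 | 0.85 |

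For d = 0.5 and 80% power, a t-test on values needs 2 × (1.96 + 0.84)² / 0.5², or 63 per level. The adjusted analysis needs 58, 48 or 33 at r = 0.3, 0.5 or 0.7. A t-test on change needs 88, 63 or 38.

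**Adding months 4 and 8, by simulation** (8,000 trials per scenario). Drop-out after months 4 and 8 follows logit P = intercept + slope × (HbA1c change since baseline at that visit). The longitudinal estimate is maximum likelihood, with month 4, then 8, then 12 regressed on factor, baseline and earlier visits. With 30% loss unrelated to response (slope 0):

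| Analysis | SE | Power for 0.5 points, Φ(0.5/SE - 1.96) |
|---|---|---|
| t-test, month-12 values | 0.262 | 48% |
| t-test, change | 0.265 | not tabulated |
| completers, baseline-adjusted | 0.230 | 59% |
| longitudinal, baseline-adjusted | 0.216 | 64% |

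Hand check on the first row: 60 × 0.7 = 42 per level, and 1.2 × √(2/42) = 0.262. The variance ratio of values t-test to model is (0.262/0.216)² = 1.47, of which about 1.29 comes from baseline and 1.14 from months 4 and 8. For change it is (0.265/0.216)² = 1.51. At 15% loss the values ratio is 1.40 (1.32 × 1.06). At correlations 0.3/0.6 it is 1.22, and at 0.6/0.8 it is 1.83. Repeat runs with other seeds put these last two at 1.21 to 1.22 and 1.85 to 1.91.

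**Bias, true effect zero.** The difference is the second level minus the first, in HbA1c points, with false-positive rates in brackets. Negative values favour the level with the heavier loss.

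| Drop-out process | Loss | t-test, values | t-test, change |
|---|---|---|---|
| Burden only (slope 0) | 28% vs 41% | 0.00 (5%) | 0.00 (5%) |
| Same response-related loss | 31% each | 0.00 (5%) | 0.00 (5%) |
| Shared slope 0.5 to 1 | 27-28% vs 40% | -0.02 to -0.04 (5%) | -0.07 to -0.11 (6-8%) |
| Slope 0 vs 0.5, low loss | 15% vs 21% | -0.03 (5.5%) | -0.11 (7%) |
| Slope 0 vs 0.5 | 30% vs 40% | -0.06 (6%) | -0.21 (12%) |
| Slope 0 vs 1 | 30% vs 41% | -0.09 (6%) | -0.36 (27%) |

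The longitudinal model is within 0.01 of zero in these runs, with about 5% false positives. The completer regression on baseline is not: it is off by -0.07 to -0.24 where response-related loss differs.

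With a true effect of -0.50 and the same drop-out slope (1) in both levels, the values t-test gives -0.48, the change t-test -0.43 and the model -0.50.

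**Where the model fails.** If drop-out depends on the unseen next value (slope 0 vs 0.5), the model is off by -0.10 (7% false positives), against -0.11 for values and -0.26 for change.

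**The case against.** A t-test is valid in a randomised factorial trial with complete data, and most of the precision gain (1.29 of 1.47) needs only baseline adjustment. That is right for precision. It does not make completer regression a substitute, because it stays biased where the longitudinal model does not.

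The bias argument is weaker than the precision argument. On month-12 values the false-positive rate hardly rises. The large figures need a t-test on change and drop-out driven by response in one level only, which nothing in the documents establishes. Dislike of diet tracking is not loss of outcome data: HbA1c, weight and PHQ-8 are collected separately, and the largest payment is for month 12. Burden alone gives no bias, and at lower loss the bias shrinks. All of this stands, so bias is the secondary point.

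The model also assumes data missing at random. When that fails it offers almost no protection relative to a t-test on values. That stands too, and is why a sensitivity analysis is needed.

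Finally, the section is in the past tense and may describe finished work. It is still the only analysis plan in the document. If results are already known, the timing must be declared.

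**Conclusion.** The concern holds and should be fixed. The omissions are plain on the page. The direction of the precision loss is secure in every setting examined; its size depends on unstated correlations and loss. It is about 1.5 times the variance in the central case, and 1.2 to 1.9 times over the correlations tried for a test on month-12 values. Reading the test as one on change does not rescue it: about 1.5 to 1.7 times.

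Bias is possible, not demonstrated. It is nil under burden-only or equal loss, small on month-12 values (up to about -0.1 points), and material on change (-0.21 to -0.36) only if response drives drop-out in one component level and not the other at 30% to 41% loss. The simulations cover HbA1c only. Weight and PHQ-8 share the same gap in the plan, but the sizes should not be carried over to them.

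**What to change.** Replace the sentence in Statistical analysis with a specification along these lines:

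- All randomised participants are analysed according to the combination they were assigned.
- Each outcome has one likelihood-based repeated-measures model: months 4, 8 and 12 as responses, the three factors each by visit, baseline value and gender as covariates, unstructured covariance.
- The month-12 contrast for each factor is the main result.
- Drop-out is tabulated by component level at each visit.
- One sensitivity analysis allows for values missing not at random, for example by shifting the missing values by a range of amounts that may differ between component levels.

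If the data have already been analysed, label this as a re-analysis specified afterwards and report it beside the t-tests.

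The cost is plan wording and modest programming, with no new participants or measurements. The price is reliance on missing at random, which the sensitivity analysis is there to test.

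### The only stated analysis is unadjusted t-tests, although each outcome's baseline is measured before randomisation and gender is the stratification factor

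*Combined protocol and SAP*

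**What the plan says.** The Statistical analysis section of the combined protocol and SAP is a single sentence: "We conducted two-sided *t*-tests to assess statistical significance and effect size", with Cohen's d as the effect size. No other section names a covariate, a regression or mixed model, or a gender term. Nor does any section say whether the tests compare follow-up values or changes.

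The design supplies what an adjusted analysis would need:

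- **Timing (Procedure):** "Once all baseline measurements had been completed, study staff randomized participants to one of the eight experimental conditions".
- **Stratification (Procedure):** "We stratified randomization by gender".
- **Baseline values (Procedure):** screening includes a home HbA1c test, the PHQ-8 and a study scale for weight. Entry requires that a participant "had a baseline HbA1c of 6.5% or higher".
- **Follow-up (Assessments):** "We measured outcomes at baseline and at 4, 8, and 12 months after baseline", for glycaemic control, weight and PHQ-8.

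The introduction makes the effect of the three add-on strategies the primary aim, and warns that "positive affect skill interventions may have small to little impact on outcomes".

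**The concern.** If the tests are ordinary two-sample tests, there are two readings, and neither makes full use of the baseline. A test on follow-up values ignores it. A test on changes subtracts it in full, which fixes the regression slope at 1 whatever the data show; in large samples this is never more precise than estimating the slope. Leaving out the stratification factor also means that the standard error takes no credit for the balance the randomisation was designed to give.

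The trial screens components, one of which is expected to have little effect. Intervals wider than the data require make it harder to tell a small effect from none, and that is the judgement on which a component is kept or dropped.

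**Working it through.** The plan states no sample size, alpha, power, target effect, SD or correlation, so it has no figure to reproduce. All numerical inputs below are assumptions, shown as ranges.

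**Notation.** ρ is the correlation between baseline and follow-up, k is the follow-up SD divided by the baseline SD, N is the total analysed with N/2 at each level of a factor, and R² is the share of outcome variance explained by gender.

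**1. Variance of the estimated effect (large sample).**

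- Adjusted against follow-up t-test: 1 − ρ². At ρ = 0.5 this is 1 − 0.25 = 0.75.
- Adjusted against change t-test, equal SDs: (1 − ρ²) / [2(1 − ρ)] = (1 + ρ)/2. At ρ = 0.7 this is 1.7/2 = 0.85.
- Adjusted against change t-test, unequal SDs: k²(1 − ρ²) / (k² + 1 − 2ρk).

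| ρ | vs follow-up | vs change, k = 1 | vs change, k = 0.8 | vs change, k = 1.25 |
|---|---|---|---|---|
| 0.3 | 0.91 | 0.65 | 0.50 | 0.78 |
| 0.5 | 0.75 | 0.75 | 0.57 | 0.89 |
| 0.7 | 0.51 | 0.85 | 0.63 | 0.98 |
| 0.9 | 0.19 | 0.95 | 0.61 | 0.95 |

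Against change scores the gain can be small. At ρ = 0.9 and k = 1, the unadjusted standard error is 1/√0.95 − 1 = 2.6% too large.

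**2. Power (noncentral t, two-sided alpha 0.05).** The follow-up t-test has effect d (in follow-up SDs) and N − 2 degrees of freedom. The adjusted model has effect d/√(1 − ρ²) and N − 6, because it fits six coefficients: intercept, three factors, baseline and gender.

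| Analysis | d = 0.2; N = 80 / 120 / 160 | d = 0.5; N = 80 / 120 / 160 |
|---|---|---|
| Follow-up t-test | 14 / 19 / 24% | 60 / 78 / 88% |
| Adjusted, ρ = 0.3 | 15 / 21 / 26% | 64 / 81 / 91% |
| Adjusted, ρ = 0.5 | 18 / 24 / 31% | 72 / 88 / 95% |
| Adjusted, ρ = 0.7 | 24 / 33 / 42% | 87 / 97 / 99% |

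In sample-size terms, for d = 0.5 and 80% power, a follow-up t-test needs 63 per factor level. The adjusted analysis needs 58, 48 or 33 at ρ = 0.3, 0.5 or 0.7.

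**3. Gender.** The unadjusted standard error is too large by 1/√(1 − R²) − 1, which is 0.5%, 1.0% or 2.6% at R² = 1%, 2% or 5%. With gender perfectly balanced, the actual alpha of a nominal 0.05 test is 2[1 − Φ(1.96/√(1 − R²))]: 0.049 at R² = 1% and 0.044 at 5%. The test is therefore slightly conservative.

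**4. Simulation under the stated randomisation.** The settings were 4000 trials each, blocks of 8 or 16 within gender, an assumed 60/40 gender split, R² = 2%, and N = 80 and 120. Adjusted-to-follow-up variance ratios were 0.92–0.93, 0.75 and 0.51–0.52 at ρ = 0.3, 0.5 and 0.7, in line with step 1. Type I error was 0.042–0.054 for the follow-up test, the change test and the adjusted model. At ρ = 0 the adjusted variance was 1.4–1.7% larger.

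**5. Cohen's d (a side point).** The plan does not say which SD is the divisor. If it is the SD of change, with equal SDs at both times, a true difference of 0.2 follow-up SDs is reported as 0.2/√[2(1 − ρ)]: 0.17, 0.20, 0.26 or 0.45 at ρ = 0.3, 0.5, 0.7 or 0.9.

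**The case against.** The strongest reply is that nothing here is wrong in the sense of biased. Assignment is randomised, the t-test is valid, its error rate is close to nominal, and the documents do not let anyone size the loss. That is correct, and the point is one of efficiency only.

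Second, the sentence may mean t-tests on changes, or on coefficients of a model that is not described. If changes are compared, the baseline is already used and the gain may be slight: at k = 1.25 and ρ = 0.7 the adjusted variance is still 98% of the unadjusted. But at k = 0.8 it is 50–63%, so this reading does not remove the point. If a model was intended, it is not stated. Entry limits on HbA1c and BMI probably also lower ρ, which favours the smaller gains against follow-up values.

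Third, gender contributes little, and no passage says that it predicts the outcomes. That stands: it belongs in the model because it shaped the randomisation, but baseline is the covariate that matters.

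Fourth, a model with three main effects raises the question of interactions. Adjusting for baseline and gender does not depend on how that is answered.

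Finally, the text is in the past tense. Covariates chosen after results are seen bring analytic choice of their own, so transparent labelling is needed.

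**Conclusion.** The point holds. The plan specifies no adjustment for baseline or gender, although both are fixed before assignment. The consequence is lost precision, not bias. Over assumed correlations of 0.3 to 0.7, adjustment leaves 91% to 51% of the variance of a follow-up comparison, and 65% to 85% of that of a change comparison with equal SDs. The benefit is useful for a moderate effect. For an effect of 0.2 SD it is modest at correlations of 0.3 to 0.5, and power stays at 42% or less for every N and correlation tabulated, so adjustment alone would not make the trial adequate for small effects. The true gain depends on the sample size, SDs and correlation, none of which is given. The change should be made, but the stated analysis is not invalid without it.

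**What to change.** For each outcome and each time point analysed, estimate the three component effects from one linear model containing the three factors, that outcome's baseline value and gender. Report adjusted mean differences with 95% confidence intervals, together with a standardised effect size whose SD is named. If t-tests are kept, state whether they compare follow-up values or changes.

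The cost is low. No new data are needed and, because baseline measurement precedes randomisation, the covariates should exist for everyone randomised and exclude nobody further. The model uses four more degrees of freedom than a two-sample t-test (N − 6 against N − 2). If baseline turned out to be unrelated to the outcome, the standard error would rise by about 1%. If results are already known, present the adjusted model as a reanalysis beside the t-tests originally reported.
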